**Rationale:**

Study I6T-MC-AMAR (AMAR) will assess the pharmacokinetics (PK), safety and tolerability of, and pain associated with, a 250-mg subcutaneous (SC) dose of LY3074828 solution formulation administered using an investigational manual pre-filled syringe (PFS) or an investigational autoinjector (AI). The administration by AI will be a 1 x 2-mL 125-mg/mL fast-speed injection and the administration by PFS will be 2 x 1-mL 125-mg/mL injections. Both methods of administration will be evaluated at 3 different injection sites (arm, thigh, and abdomen) in order to expand the options for administration in patient use. The study will provide data to bridge PFS administration (as used in Study I6T-MC-AMAE [AMAE]) of LY3074828, a monoclonal antibody, with the investigational AI device planned for use in subsequent studies and patient use.

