## 5. Study Design

### 5.1. Overall Design

Study I6T-MC-AMAR (AMAR) is a single-center, randomized, parallel-arm, open-label, Phase 1 single-dose study of LY3074828 solution formulation in healthy subjects.

Pharmacokinetics, safety and tolerability of, and pain associated with, 250-mg SC doses administered using a PFS or AI at 3 different injection sites will be evaluated.

**Screening Period ( $\leq 28$  days):** Subjects will be evaluated for study eligibility  $\leq 28$  days prior to enrollment.

**Residential Period (2 days):** A total of approximately 66 subjects who fulfill the eligibility criteria will be randomized to 1 of 6 dosing regimen arms, with 11 subjects randomized to each arm to ensure completion of 10 subjects in each:

- Test 1: 250 mg LY3074828 solution formulation, 1 x 2-mL 125-mg/mL AI injection, administered in the arm
- Test 2: 250 mg LY3074828 solution formulation, 1 x 2-mL 125-mg/mL AI injection, administered in the thigh
- Test 3: 250 mg LY3074828 solution formulation, 1 x 2-mL 125-mg/mL AI injection, administered in the abdomen
- Reference 1: 250 mg LY3074828 solution formulation, 2 x 1-mL 125-mg/mL PFS injections targeting a 5- to 10-second injection time for each injection, administered in the arm
- Reference 2: 250 mg LY3074828 solution formulation, 2 x 1-mL 125-mg/mL PFS injections targeting a 5- to 10-second injection time for each injection, administered in the thigh
- Reference 3: 250 mg LY3074828 solution formulation, 2 x 1-mL 125-mg/mL PFS injections targeting a 5- to 10-second injection time for each injection, administered in the abdomen

Subjects will report to the clinical research unit (CRU) on Day -1 and will remain at the CRU until the scheduled procedures have been completed on Day 2. Study drug will be administered by investigative site staff by SC injection per the randomization scheme in the morning of Day 1 after an overnight fast.

**Outpatient Follow-up Period (12 weeks):** The follow-up period will include outpatient visits for a total of 12 weeks (Days 4, 8, 11, 15, 22, 29, 43, 57, 71, and 85) following dose administration on Day 1 to assess the PK, safety and tolerability of, and pain associated with LY3074828 PFS and AI administrations. Assessment of pain at the Follow-up visits does not include visual analog scale (VAS) score.

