### **10.3.2. Pharmacokinetic Analyses**

#### **10.3.2.1. Pharmacokinetic Parameter Estimation**

Pharmacokinetic parameter estimates for LY3074828 will be calculated by standard noncompartmental methods of analysis.

The primary parameters for analysis will be  $AUC(0-\infty)$ ,  $AUC(0-t_{last})$ , and  $C_{max}$  for LY3074828. The secondary parameter for analysis will be the time to maximum observed drug concentration ( $t_{max}$ ) of LY3074828. Other noncompartmental parameters, such as half-life associated with the terminal rate constant ( $t_{1/2}$ ), apparent total body clearance of drug calculated after extra-vascular administration (CL/F), and apparent volume of distribution during the terminal phase after extra-vascular administration ( $V_z/F$ ), may be reported.

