8.3 Pharmacokinetic Assessment

8.3.1 Pharmacokinetic Analysis

PK parameter estimates will be determined using non-compartmental procedures in validated software program (Phoenix WinNonlin Version 6.4 or later).

Serum concentrations of LY3074828 will be used to determine the following PK parameters, when possible:

| Parameter | Units | Definition |
|----------------------------|-----------|-----------------------------------------------------------------------------------------------------------------------------------------|
| AUC(0-t _{last}) | µg*day/mL | area under the concentration versus time curve from time zero to time t, where t is the last time point with a measurable concentration |
| AUC(0-∞) | µg*day/mL | area under the concentration versus time curve from time zero to infinity |
| %AUC(t _{last} -∞) | % | percentage of AUC(0-∞) extrapolated |
| C _{max} | µg/mL | maximum observed drug concentration |
| t _{max} | day | time of maximum observed drug concentration |
| t _{1/2} | day | half-life associated with the terminal rate constant (λ_z) in non-compartmental analysis |
| CL/F | L/day | apparent total body clearance of drug calculated after extra-vascular administration |
| V _{Z/F} | L | apparent volume of distribution during the terminal phase after extra-vascular administration |
| V _{ss/F} | L | apparent volume of distribution at steady state after extra-vascular administration |

Additional PK parameters may be calculated, as appropriate. The software and version used for the final analyses will be specified in the CSR. Any exceptions or special handling of data will be clearly documented within the final study report.

Formatting of tables, figures and abbreviations will follow the Eli Lilly Global PK/PD/TS Tool: NON-COMPARTMENTAL PHARMACOKINETIC STYLE GUIDE. The version of the tool effective at the time of PK analysis will be followed.

General PK Parameter Rules

- Actual sampling times will be used in the final analyses of individual PK parameters, except for non-bolus pre-dose sampling times which will be set to zero. For non-bolus, multiple dose profiles, the pre-dose time will be set to zero unless a time deviation falls outside of the protocol blood collection time window which is considered to impact PK parameter derivation.

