10. CHANGES FROM THE PROTOCOL SPECIFIED STATISTICAL ANALYSES

There were no changes from the protocol specified statistical analyses.

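### SAP 8.3.1 lists Vss/F for non-compartmental estimation from subcutaneous data alone; by the usual route the value is biased upward by the mean absorption time

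*SAP*

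**What the plan says.** SAP 8.3.1 (Pharmacokinetic Analysis) sets the method: "PK parameter estimates will be determined using non-compartmental procedures in validated software program". It then introduces its parameter table with "Serum concentrations of LY3074828 will be used to determine the following PK parameters, when possible". One row of that table is Vss/F, "apparent volume of distribution at steady state after extra-vascular administration". The section gives no formula for Vss/F, lists neither mean residence time nor mean absorption time, and contains no correction for absorption and no caveat.

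The route is subcutaneous in every arm. Protocol 5.1 states: "Study drug will be administered by investigative site staff by SC injection per the randomization scheme". The arms differ in device and injection site, and none is intravenous.

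Protocol 10.3.2.1 makes AUC(0-∞), AUC(0-tlast) and Cmax primary and tmax secondary. It then allows further parameters to be reported: "Other noncompartmental parameters, such as half-life associated with the terminal rate constant", followed by CL/F and Vz/F. The only volume it names is Vz/F, "apparent volume of distribution during the terminal phase after extra-vascular administration".

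The inferential analyses in SAP 8.3.2 cover the two AUCs, Cmax and tmax. Vss/F is not among them.

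**The concern.** Non-compartmental Vss is clearance multiplied by the mean residence time of drug in the body once it has entered the circulation. After a subcutaneous dose, the residence time computed from the concentration curve also counts the time spent at the injection site. Without intravenous data the two parts cannot be separated, so the product is not the quantity its label claims. More subjects or denser sampling would not cure this, because it is a bias and not imprecision.

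What is at stake is one reported parameter whose level would be wrong in a known direction. Someone taking a steady-state volume for this antibody from the study report would take one that is too large.

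**Working it through.** The plan states no figure for Vss/F, so there is none to reproduce. The check has four parts.

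**1. The identity.** Write MRT for the disposition mean residence time, MAT for the mean absorption time and AUMC for the area under the first-moment curve.

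- Intended quantity: Vss/F = (CL/F) × MRT.
- Available after a subcutaneous dose: AUMC/AUC = MRT + MAT.
- Hence the computed value is (CL/F) × (MRT + MAT) = Vss/F + (CL/F) × MAT.
- Relative inflation = MAT / MRT, which cannot be negative.

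**2. Size.** The documents give no elimination half-life and no absorption rate, so these are assumptions: one-compartment disposition, elimination half-life (t½) 7 to 20 days, and first-order absorption rate constant ka 0.15 to 0.6/day. Then MAT = 1/ka, MRT = t½/ln 2, and inflation = (1/ka)/(t½/ln 2).

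| t½ (days) | ka (/day) | MAT (days) | MRT (days) | Inflation |
|---|---|---|---|---|
| 7 | 0.15 | 6.67 | 10.10 | 66% |
| 10 | 0.2 | 5.00 | 14.43 | 35% |
| 14 | 0.4 | 2.50 | 20.20 | 12% |
| 20 | 0.6 | 1.67 | 28.85 | 6% |

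The 66% pairs the shortest assumed half-life with the slowest assumed absorption, and the 6% is the opposite corner. The size depends on these assumptions; the direction does not.

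**3. Numerical check at the planned sampling times.** Profiles were simulated at 0, 2, 6 and 24 hours and at the outpatient days to Day 85, and analysed with the SAP's linear-then-logarithmic trapezoidal rule and extrapolation from observed Clast. True V/F was set at 10 L, with elimination half-life 7 to 21 days and absorption half-life 0.5 to 4 days.

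- Worked case, elimination half-life 10 days and absorption half-life 2 days: analytic CL/F = 10 × 0.693/10 = 0.693 L/day and residence time = (10 + 2)/0.693 = 17.3 days, giving 12.0 L. The simulated analysis gave CL/F 0.703 and residence time 17.5 days, hence 12.3 L.
- Over all one-compartment scenarios, computed Vss/F ran from 10.3 to 16.2 L against the true 10 L. Vz/F ran from 10.05 to 10.28 L.
- Two-compartment runs (central 6 L, peripheral 4 L, true Vss/F 10 L, same disposition MRT as half-lives of 7 to 14 days, absorption half-life 1 to 4 days) gave 10.9 to 16.2 L. In several, computed Vss/F exceeded Vz/F, for example 13.31 against 11.45 L. True volumes cannot stand in that order.

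**4. How far a device difference in absorption could move it.** With CL, V and F identical and absorption half-lives a and b on the two devices, the Vss/F ratio is (1 + b/t½)/(1 + a/t½).

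| t½ (days) | 2 v 3 days | 2 v 4 days |
|---|---|---|
| 7 | 1.11 | 1.22 |
| 10 | 1.08 | 1.17 |
| 14 | 1.06 | 1.13 |

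For scale, take the 55% geometric CV of Protocol 10.1 and assume that it also applies to Vss/F. The log SD is √ln(1 + 0.55²) = 0.514. The 90% CI half-width at that SD would be 1.673 × 0.514 × √(2/30) = 0.22 pooled over sites (56 df) and 1.734 × 0.514 × √(2/10) = 0.40 within a site (18 df). The largest ratio in the table is ln 1.22 = 0.20 on the same scale.

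**The case against.** **The formula is inferred.** This is true. The SAP does not say how Vss/F will be computed, and clearance times residence time is only the standard non-compartmental route. But no other route is described and no intravenous input is mentioned. The qualifier in "Serum concentrations of LY3074828 will be used to determine the following PK parameters, when possible" permits omission without requiring it. Software would still produce a number, so the value is computable but mislabelled.

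**It is an undeclared change from the protocol.** A reader might infer this by setting the added row against the SAP section 10 statement, "There were no changes from the protocol specified statistical analyses". The documents do not support that reading. The list in Protocol 10.3.2.1 is given by example, Protocol 10.3.2.2 allows additional PK analyses, and the SAP introduction undertakes to flag only substantial differences. One more descriptive parameter falls within that latitude.

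**It would mislead the device bridge.** The Protocol synopsis says "The study will provide data to bridge PFS administration", so a reader might fear that slower absorption with one device would pass for a larger distribution volume. This claims too much. No comparison of Vss/F is planned, and by-arm reporting is only likely, because the output shells are a separate document. Cmax and tmax, which respond directly to absorption, are compared between devices overall and by site. The artefact is also modest against the expected noise. That argument limits the device contrast; it does not correct the level of Vss/F, which is biased in every arm.

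**Vz/F is not immune either.** This stands in part. CL/F and Vz/F both scale with 1/F, and Protocol 5.5 puts subcutaneous bioavailability at about 40% in an earlier study, so a device or site difference in F would shift both. Removing Vss/F removes only the absorption-time term.

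**A footnote would do.** A footnote would warn the reader, but the number would still not be the quantity named in the table.

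**Conclusion.** The point holds as a minor one. SAP 8.3.1 lists a parameter that subcutaneous data alone cannot estimate, and nothing in the documents supplies the missing intravenous information or limits the interpretation. Given the standard formula, the reported value is biased upward by MAT/MRT: about 6% to 66% over the assumed half-lives and absorption rates, and 12% to 35% for half-lives of 10 to 14 days with ka 0.2 to 0.4/day. The direction follows from the identity and is secure. The size is conditional on figures that the documents do not give.

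The consequence is confined to a descriptive volume. The AUC and Cmax ratios and the tmax comparison do not use it, and no objective depends on it.

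**What to change.** Delete the Vss/F row from the SAP 8.3.1 parameter table, its entry in the SAP abbreviation list, and any matching line in the output shells. Keep CL/F and Vz/F, which the protocol names and which contain no residence-time term, and read them as scaled by 1/F.

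If the sponsor prefers to keep Vss/F, SAP 8.3.1 should state the formula, name the source of the intravenous disposition residence time, and describe how absorption time will be subtracted. Borrowing that time from another study assumes comparable disposition in the two populations, and the SAP should say so.

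Deletion costs one table row and its cross-references. It needs no change to sampling, data collection, sample size or the planned comparisons.

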8.3.2 Pharmacokinetic Statistical Methodology

The AUC(0- ∞), AUC(0- t_{last}), and C_{max} will be log-transformed and analyzed using a linear fixed-effects model. The model will include device and injection location as fixed effects. The differences between the AI (Test) and PFS (Reference) will be back-transformed to present the ratios of geometric least squares (LS) means and the corresponding 90% CI.

Example SAS code:

```
proc mixed data=test alpha=0.1;
  class device location;
  model log_pk = device location / ddfm=kr alpha=0.1;
  lsmeans device / pdiff cl alpha=0.1;
  ods output lsmeans=lsmeans;
  ods output diffs=diffs;
run;
```

The t_{max} of LY3074828 will be analyzed using a non-parametric method. Estimates of the median difference between AI (Test) and PFS (Reference), 90% CIs, and p-values from the Wilcoxon rank sum test will be calculated.

The above analyses will also be repeated for each location separately.

Additional PK analyses may be conducted if deemed appropriate.

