## 2. Schedule of Activities

## Study Schedule Protocol I6T-MC-AMAR

Procedure	Screening ≤28 days	Days															Comments
		-1	1	2	4 ±1d	8 ±1d	11 ±1d	15 ±2d	22 ±2d	29 ±2d	43 ±2d	57 ±3d	71 ±3d	85/ED ±3d			
Informed consent	X																
Review / confirm inclusion/exclusion criteria	X	X															Any time prior to dosing.
Subject admission to CRU		X															
Subject discharge from CRU				X													
Outpatient visit	X				X	X	X	X	X	X	X	X	X	X			
Randomization			X														Subjects randomized to 1 of 6 dosing regimen arms.
LY3074828 injection			X														Doses administered by investigative site staff.
Stopwatch recording			X														Stopwatch is the source for injection duration capture for PFS and AI.
Medical history	X																
Weight, height, and BMI	X																
Vital signs: blood pressure, pulse rate, temperature (hour)	X	X	0, 6	24	X	X	X	X	X	X	X				X		Times with respect to start of dosing. Single ECGs to be collected. Zero-hour collection within 30 minutes before dosing. Time allowance for 6- and 24-hour time points: ±30 and ±90 minutes, respectively. For vital sign assessments, temperature need only be included at predose and when clinically indicated.
12-lead ECG (hour)	X		0	24											X		
Physical examination / medical assessment	X	X		X									X		X		Full physical examination/medical assessment at screening. Symptom-directed physical examination/medical assessment at all other time points, and as deemed necessary by the investigator.

Procedure	Screening ≤28 days	Days															Comments
		-1	1	2	4 ±1d	8 ±1d	11 ±1d	15 ±2d	22 ±2d	29 ±2d	43 ±2d	57 ±3d	71 ±3d	85/ED ±3d			
AE review	X	X	X	X	X	X	X	X	X	X	X	X	X	X	X	AE only after signing ICF. Product complaints and device-related AEs collected as appropriate.	
QuantiFERON®-TB Gold test	X																
Serology	X															See Appendix 2 for test details.	
Ethanol test and urine drug screen	X	X														May be repeated at the discretion of the investigator. Ethanol test may be measured in blood, urine, or expired air. See Appendix 2 for test details.	

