#### 10.2.2. Study Participant Characteristics

The subject's age, sex, weight, BMI, height, race/subrace, and other demographic data will be summarized by dosing regimen and overall.

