3. INTRODUCTION

This SAP has been developed after review of the Clinical Study Protocol (final version dated 11 June 2018) and protocol amendment (a) (final version dated 13 September 2018).

This SAP describes the planned analysis of the safety, tolerability and pharmacokinetic (PK) data from this study. A detailed description of the planned TFLs to be presented in the clinical study report (CSR) is provided in the accompanying TFL shell document.

The intent of this document is to provide guidance for the statistical and PK analyses of data. In general, the analyses are based on information from the protocol, unless they have been modified by agreement between Eli Lilly and Company and Covance Early Clinical (EC) Biometrics. A limited amount of information concerning this study (e.g., objectives, study design) is given to help the reader's interpretation. This SAP must be signed off prior to first subject administration for this study. When the SAP and TFL shells are agreed upon and finalized, they will serve as the template for this study's CSR.

This SAP supersedes the statistical considerations identified in the protocol; where considerations are substantially different, they will be so identified. If additional analyses are required to supplement the planned analyses described in this SAP, they may be performed and will be identified in the CSR. Any substantial deviations from this SAP will be agreed upon between Eli Lilly and Company and Covance EC Biometrics and identified in the CSR. Any minor deviations from the TFLs may not be documented in the CSR.

This SAP is written with consideration of the recommendations outlined in the International Council on Harmonisation (ICH) E9 Guideline entitled Guidance for Industry: Statistical Principles for Clinical Trials¹ and the ICH E3 Guideline entitled Guidance for Industry: Structure and Content of Clinical Study Reports².

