7. SAMPLE SIZE JUSTIFICATION

Approximately 66 subjects will be enrolled with a target of 60 subjects completing the study (10 completers per treatment).

Data from AMAL (2 x 1-mL doses of 250 mg LY3074828) and AMAE (2 x 1-mL PFS doses of 250 mg LY3074828) studies showed that the geometric coefficient of variation (CV) ranged from 55% to 40% for the PK measurements (ie, area under the concentration versus time curve [AUC] from time zero to infinity [AUC($0-\infty$)], AUC from time zero to time t , where t is the last sample with a measurable concentration [AUC($0-t_{last}$)], and maximum observed drug concentration [C_{max}]). Thus, the geometric CV was assumed to be 55% when calculating precision.

A sample size of 60 subjects will provide a precision (ie, half-width of 90% of confidence interval [CI] with a coverage probability of 90%), in log scale, of approximately 0.48 for the geometric means ratio of reference versus test for AUC($0-\infty$), AUC($0-t_{last}$), and C_{max} . Equivalently, there is a 90% probability that the distance between the lower limit of the 90% CI and the point estimate of the geometric means ratio is not larger than 38%.

Subjects who are randomized but not administered treatment, or subjects (maximum of 2 subjects per dose regimen arm) that are administered treatment but do not have PK and anti-drug antibody (ADA) samples collected up to and including Day 57, may be replaced to ensure that approximately 10 subjects from each treatment arm may complete the study.

DEFINITION OF ANALYSIS POPULATIONS

The “Safety” population will consist of all subjects receiving a dose of LY3074828, whether or not they completed all protocol requirements.

The “Pharmacokinetic” population will be conducted on the full analysis set and consists of all randomized subjects receiving the dose of LY3074828 and have evaluable PK data.

All protocol deviations that occur during the study will be considered for their severity/impact and will be taken into consideration when subjects are assigned to analysis populations.

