8.2 Demographics and Subject Disposition

Subject disposition will be listed. The demographic variables age, sex, race, ethnicity, body weight, height and body mass index will be summarized by treatment arm and overall as well as being listed. All other demographic variables will be listed only.

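### Cheap improvement, not an error: log body weight, already measured at screening, could be prespecified as a covariate in the pooled AI:PFS models for AUC and Cmax

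*SAP*

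**What the plan says.** SAP 8.3.2 gives the model for the three log-transformed primary PK parameters: "The model will include device and injection location as fixed effects". Protocol 10.3.2.2 uses the same terms, and the SAP's example code agrees: "model log_pk = device location / ddfm=kr alpha=0.1". The output is a ratio of geometric LS means, AI to PFS, with a 90% CI. SAP 8.3.2 then adds: "The above analyses will also be repeated for each location separately".

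The Schedule of Activities in Protocol Section 2 has a screening row for "Weight, height, and BMI". The only planned uses of weight are descriptive. Protocol 10.2.2 says that "weight, BMI, height, race/subrace, and other demographic data will be summarized by dosing regimen and overall", and SAP 8.2 says that "body weight, height and body mass index will be summarized by treatment arm and overall". Neither document names weight as a covariate, and Protocol 7.2 names no stratification factor.

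On variability, SAP Section 7 says: "Thus, the geometric CV was assumed to be 55% when calculating precision". The range quoted there from earlier studies is 40% to 55%. On timing, SAP Section 3 says: "This SAP must be signed off prior to first subject administration for this study".

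**The concern.** Every subject receives the same 250 mg dose, and inclusion criterion 3 allows a BMI of 18.0 to 32.0 kg/m², so dose per kilogram differs between subjects. That is a reason, taken from the documents, to consider weight before other baseline variables. It does not show how strongly weight affects exposure.

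The design is parallel-group, so between-subject variability sets the width of the CI for the AI:PFS ratio. If weight explains part of that variability, leaving it out gives up precision and lets a chance difference in weight between the device groups move the ratio. Both documents also allow further PK analyses that they do not specify. A weight-adjusted ratio could therefore be added after the data are seen, with no prior statement of which ratio is the main one.

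**Working it through.** **Inputs from the documents.** 60 completers, 10 per arm, so 30 AI v 30 PFS pooled. 90% CI. CV 55% for planning, 40% at the low end. Log-scale SD = √ln(1 + CV²): √ln(1.3025) = 0.514 at 55% and √ln(1.16) = 0.385 at 40%.

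**Assumptions not in the documents.** SD of log weight 0.15 to 0.20. Slope of log exposure on log weight from 0 to -1.

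**1. The plan's own precision figure.** The half-width met with 90% assurance is t(0.95, df) × SD × √(2/n) × √(χ²(0.90, df)/df).
- 10 v 10, df 18: 1.734 × 0.514 × √(2/10) = 0.399; × 1.202 = 0.479. Then 1 − exp(−0.479) = 38.1%. This matches the stated 0.48 and 38%, so the stated figure describes one by-location comparison.
- Pooled model, 30 v 30, df 60 − 4 = 56: 1.6725 × 0.514 × √(2/30) = 0.222; with assurance, 0.248.

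The baseline for the pooled models is therefore 0.222, not 0.48.

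**2. Cost of one covariate with no prognostic value.** Width ratio = [t(0.95, df − 1)/t(0.95, df)] × √(1 + 1/(df − 2)).
- Pooled: 1.0003 × √(1 + 1/54) = 1.0003 × 1.0092 = 1.0095, or +0.95%.
- By location: 1.0032 × √(1 + 1/16) = 1.0032 × 1.0308 = 1.034, or +3.4%.

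**3. Gain.** Multiply by √(1 − R²), where R² = (slope × SD of log weight / log-scale SD)². Example at CV 55%, slope -1, SD 0.20: R² = (0.20/0.514)² = 0.151; 1.0095 × √0.849 = 0.930, or -7.0%.

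| Slope | Pooled, CV 55% | Pooled, CV 40% | By location, CV 55% |
|---|---|---|---|
| 0 | +0.95% | +0.95% | +3.4% |
| -0.5 | -0.1 to -1.0% | -1.0 to -2.5% | +2.3 to +1.4% |
| -1 | -3.4 to -7.0% | -7.0 to -13.7% | -1.1 to -4.7% |

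The best pooled case at CV 55% takes the half-width from 0.222 to 0.222 × 0.930 = 0.206. Around a ratio of 1, the CI goes from 0.80–1.25 to 0.81–1.23.

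**4. Break-even.** R² = 1 − 1/(width ratio)².
- Pooled: 1 − 1/1.0095² = 1.9% of variance. This is an absolute slope of 0.35 to 0.47 at CV 55%, or 0.26 to 0.35 at CV 40%.
- By location: 6.5% of variance, an absolute slope of 0.65 to 0.87 at CV 55%.

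**5. Spread around the average.** The pooled model was simulated with and without log weight at CV 55% and SD of log weight 0.18.
- Slope 0: mean change about +0.95%. The CI narrowed in 20% of trials, widened by more than 1% in 45%, and widened by more than 2.8% in one in ten.
- Slope -0.5: mean about -0.6%; narrowed in 50%.
- Slope -1: mean about -5.4%; narrowed in 89%.

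Over the assumed ranges, coverage of the 90% CI was 0.893 to 0.907 with and without weight.

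**The case against.** The strongest case against is that nothing here is broken. Protocol and SAP agree on the model, randomization makes the unadjusted ratio valid, and no equivalence margin is stated, so no stated decision changes. The benefit rests on a slope that the documents do not give; at slope -0.5 and CV 55% the CI narrows in only about half of trials. The pooled assured half-width of 0.248 is already about half the planned 0.48. Further PK analyses are permitted anyway, and the SAP carries approvals dated 19 to 25 September 2018, so adding a term means revising it.

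Most of this stands, and it sets the limits of the point. A reader might infer that omitting weight biases the ratio or makes the planned analysis deficient. The documents do not support that. A reader might also infer an assured gain, or a loss that can never exceed 1%. Neither holds: the gain is conditional, and the 1% is an average that chance weight imbalance can exceed in the one trial that is run.

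Two parts of the objection do not remove the point. General permission for additional analyses does not fix in advance which ratio is the main one. Meeting a precision target set for 10 v 10 comparisons is no reason to pass over a low-cost baseline adjustment in the pooled models.

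**Conclusion.** The point holds as an optional improvement of low severity. The pooled PK models leave out a baseline measurement that the trial already collects. The mean effect of adding it runs from a CI about 1% wider if weight is not prognostic to one 3 to 7% narrower (CV 55%) or 7 to 14% narrower (CV 40%) at slope -1. Adjustment pays on average once weight explains more than about 1.9% of the variance in log exposure.

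These figures rest on 60 completers, the documents' CVs, and the assumed SD of log weight and slopes. Whether weight reaches break-even for this antibody cannot be settled from the documents. The case for prespecifying which ratio is the main one does not depend on the slope.

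**What to change.** Before any PK data are seen:
- Add the log of screening body weight as a continuous covariate to the pooled models for AUC(0-∞), AUC(0-tlast) and Cmax: `model log_pk = device location log_weight`.
- State in advance which pooled ratio is the main one, preferably the adjusted one, and report the other alongside it.
- Leave the 10 v 10 by-location models unadjusted, because break-even is much higher there.
- Record the change in SAP Section 10, which at present reports no changes from the protocol analyses.

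The cost is one model term, one error degree of freedom, one extra output column and a minor revision of an approved SAP. No new data are needed. The statistical downside is a pooled CI about 1% wider on average if weight is not prognostic, and sometimes more in a single trial.
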